4.2 Exclusion Criteria**4.2.1 Pregnancy or Breast-Feeding**

Pregnant or breast-feeding women will not be entered on this study because there is yet no available information regarding human fetal or teratogenic toxicities. Pregnancy tests must be obtained in girls who are post-menarchal. Males or females of reproductive potential may not participate unless they have agreed to use a highly effective method of contraception during protocol therapy and for at least 3 months after the last dose of ramucirumab. A highly effective method of contraception is defined as one that results in a low failure rate (that is, $<1\%$ per year) when used consistently and correctly. Barrier methods used alone are not highly effective methods of contraception. For female patients, if a barrier method is used, a hormonal method must be used with it to ensure that pregnancy does not occur. Abstinence is an acceptable method of birth control. Those who become pregnant while on treatment with ramucirumab must discontinue immediately and consult their treating physician.

4.2.2 Concomitant Medications

4.2.2.1 Corticosteroids: Patients receiving corticosteroids who have not been on a stable or decreasing dose of corticosteroid for at least 7 days prior to enrollment are not eligible.

4.2.2.2 Investigational Drugs: Patients who are currently receiving another investigational drug are not eligible.

THIS PROTOCOL IS FOR RESEARCH PURPOSES ONLY, SEE PAGE 1 FOR USAGE POLICY

4.2.2.3 Anti-cancer Agents: Patients who are currently receiving other anti-cancer agents are not eligible.

4.2.2.4 Anti-GVHD agents post-transplant:

Patients who are receiving cyclosporine, tacrolimus or other agents to prevent graft-versus-host disease post bone marrow transplant are not eligible for this trial.

4.2.2.5 Anti-inflammatory agents: Patients who are chronically receiving aspirin, ibuprofen or other non-steroidal anti-inflammatory drugs are not eligible.

4.2.2.6 Anti-platelet agents: Patients who are currently receiving anti-platelet agents are not eligible.

4.2.2.7 Anti-hypertensives:

Patients who are receiving anti-hypertensive medications for control of blood pressure at the time of enrollment are not eligible for this trial.

4.2.2.8 Anti-coagulation: Patients who are currently receiving therapeutic anti-coagulation with heparin, low-molecular weight heparin or coumadin are not eligible for this trial.

4.2.2.9 Belimumab: Patients who are currently receiving belimumab (a monoclonal antibody for systemic lupus erythematosus) are not eligible.

4.2.2.10 Bisphosphonate derivatives: Patients who are currently receiving bisphosphonate derivatives are not eligible.

4.2.3 Surgery: Patients who have had or are planning to have the following invasive procedures are not eligible:

- Major surgical procedure, laparoscopic procedure, open biopsy or significant traumatic injury within 28 days prior to enrollment.
- Central line placement or subcutaneous port placement is not considered major surgery. External central lines must be placed at least 3 days prior to enrollment and subcutaneous ports must be placed at least 7 days prior to enrollment
- Core biopsy within 7 days prior to enrollment.
- Fine needle aspirate within 7 days prior to enrollment.
- Surgical or other wounds must be adequately healed prior to enrollment

NOTE: For purposes of this study, bone marrow aspirate and biopsy are not considered surgical procedures and therefore are permitted within 14 days prior to start of protocol therapy.

4.2.4 Bleeding and Thrombosis:

- Patients with evidence of active bleeding: intratumoral hemorrhage by current imaging, or bleeding diathesis are not eligible.
- Patients with known or prior history in prior 3 months of esophageal varices are not eligible.

THIS PROTOCOL IS FOR RESEARCH PURPOSES ONLY, SEE PAGE 1 FOR USAGE POLICY

- Patients with a history of CNS arterial/ venous thromboembolic events including transient ischemic attack (TIA) or cerebrovascular accident (CVA) within 6 months prior to study enrollment are not eligible.
- Patients with a history of deep vein thrombosis (including pulmonary embolism) within 3 months prior to study enrollment are not eligible.
- Patients with a history of hemoptysis or other signs of pulmonary hemorrhage within 3 months prior to study enrollment are not eligible.
- Patients with a history of \geq Grade 3 bleeding disorders, vasculitis, or had a significant (\geq Grade 3) episode from gastrointestinal bleeding, within 6 months prior to enrollment are not eligible.
- For Part B: Patients with CNS tumors and evidence of new CNS hemorrhage of more than punctate size and/or more than three foci of punctate hemorrhage on baseline MRI obtained within 14 days prior to study enrollment are not eligible. Note: ECHO Gradient MRI sequences per institutional guidelines are required for patients with CNS tumors

- 4.2.5 Patients with known cardiac disease per the New York Heart Association definition such as myocardial infarction, severe or unstable angina, peripheral vascular disease, or congestive heart failure or peripheral vascular disease are not eligible.
- 4.2.6 Patients who have a history of fistula, gastrointestinal ulcer or perforation, or intra-abdominal abscess within 3 months of study enrollment are not eligible.
- 4.2.7 Patients with a history of hypertensive crisis or hypertensive encephalopathy within 6 months of study enrollment are not eligible.
- 4.2.8 Patients who have non-healing wound, unhealed or incompletely healed fracture, or a compound (open) bone fracture at the time of enrollment are not eligible.
- 4.2.9 Immunocompromised patients (other than that related to the primary oncologic diagnosis or to the use of corticosteroids) including patients known to be HIV positive are not eligible.
- 4.2.10 Infection: Patients who have an uncontrolled infection are not eligible.
- 4.2.11 Patients who have received a prior solid organ transplantation are not eligible.
- 4.2.12 Patients who in the opinion of the investigator may not be able to comply with the safety monitoring requirements of the study are not eligible.

5.0 TREATMENT PROGRAM

5.1 Overview of Treatment Plan

Treatment Schedule Table		
Day	Ramucirumab (i.v. over 60 minutes)	Disease Evaluation
1	X	
15	X	

THIS PROTOCOL IS FOR RESEARCH PURPOSES ONLY, SEE PAGE 1 FOR USAGE POLICY

29	X	
42		X

A cycle of therapy is considered to be 42 days. A cycle may be repeated for a total of 8 cycles, up to a total duration of therapy of approximately 12 months. This is an open-label study.

Effort should be made to begin protocol therapy on Monday through Thursday if possible to accommodate correlative sample shipments.

Drug doses should be adjusted based on actual weight measured within 7 days prior to the beginning of each cycle.

Update: With the release of Amendment #2A, the dose escalation portion of the study is complete. Given this, Part B will open to patients with relapsed or refractory CNS tumors.

5.2 Criteria for Starting Subsequent Cycles

A cycle may be repeated every 42 days if the patient has at least stable disease and has again met laboratory parameters as defined in the eligibility section, [Section 4.0](#).

5.3 Dose Escalation Schema (Completed)

5.3.1 Inter-Patient Escalation for Part A:

Part A of the study is an open-label, Phase 1, dose-escalation study. Ramucirumab will be administered as an intravenous infusion over 60 minutes every other week for 3 infusions over a 6-week period constituting a cycle. The anticipated maximum number of evaluable subjects required to complete Part A is 24 patients (See [Section 11.1](#)).

Patients should receive diphenhydramine (1 mg/kg, maximum dose 50 mg) (or alternative antihistamine) within 30 to 60 minutes prior to each infusion with ramucirumab. Anaphylactic precautions should be observed during ramucirumab administration. If \geq Grade 2 infusional reaction occurs, the infusion should be stopped and supportive care given as per institutional guidelines.

See [Section 6.3](#) for management and dose modification guidelines for infusional reactions (IRR). For the first infusion, vital signs should be monitored prior to infusion, every 30 (\pm 5) minutes during the infusion, and every 30 (\pm 5) minutes for a one-hour observation period after the completion of the infusion. If there is no evidence of an IRR during the initial 2 infusions of ramucirumab, then no observation period is required for subsequent treatment cycles. In the event an IRR occurs thereafter, then the one-hour observation period should be reinstated.

The starting dose of ramucirumab will be 8 mg/kg (dose level 1) with dose levels for subsequent groups of patients as follows.

Dose Level	Dose (mg/kg)
------------	--------------

THIS PROTOCOL IS FOR RESEARCH PURPOSES ONLY, SEE PAGE 1 FOR USAGE POLICY

-1	6
1*	8
2	12
3^	≤ 16

* Starting Dose Level

^ Escalation to Dose level 3 will only be considered after evaluation of PK and toxicity at dose Level 2. If $C_{min,ss}$ of $\geq 50 \mu\text{g/mL}$ has not been achieved in at least 5 out of 6 evaluable patients from dose level 2, and if the MTD has not yet been reached, then dose level 3 will be considered.

Ramucirumab will be provided by Eli Lilly and Company. Do not use commercial supply.

There will be no escalations beyond dose level 3 (16 mg/kg). If the MTD has been exceeded at the first dose level, then the subsequent cohort of patients will be treated at a dose of 6 mg/kg (dose level -1). If dose level -1 is not well tolerated, further de-escalation will not occur. The study will be closed to accrual.

Defining RP2D: After accrual to dose level 2 is completed, PK comparisons from dose levels 1 and 2 will be performed. An expansion cohort will accrue at the lowest tolerable dose at which C_{min} of $\geq 50 \mu\text{g/mL}$ has been achieved in at least 5 out of 6 evaluable patients to acquire PK data in a representative number of young patients (i.e. patients < 12 years old). If at least 10 out of the total 12 evaluable patients have a steady state concentration of ramucirumab greater than $50 \mu\text{g/mL}$, then the RP2D has been defined. If $C_{min,ss}$ of $\geq 50 \mu\text{g/mL}$ has not been achieved in at least 5 out of 6 evaluable patients from dose level 2, and if the MTD has not yet been reached, then dose level 3 will be considered.

Update: The RP2D was determined to be 12 mg/kg.

5.3.2 **Part B:** Once the RP2D has been determined in Part A, Part B will open to enroll children with relapsed or refractory CNS tumors who will receive ramucirumab at the MTD or RP2D. Part B of the study will require up to 6 evaluable patients enrolled at the MTD or RP2D as determined in Part A (See [Section 11.1](#)).

5.3.3 **Intra-Patient Escalation**

Intra-patient dose escalation is not allowed.

5.4 **Grading of Adverse Events**

Adverse events (toxicities) will be graded according to the NCI Common Terminology Criteria for Adverse Events (CTCAE) version 5.0. All appropriate treatment areas should have access to a copy of the CTCAE version 5.0. A copy of the CTCAE version 5.0 can be downloaded from the CTEP web site http://ctep.cancer.gov/protocolDevelopment/electronic_applications/ctc.htm. Any suspected or confirmed dose-limiting toxicity should be reported immediately (within 24 hours) to the Study Chair.

5.5 **Definition of Dose-Limiting Toxicity (DLT)**

DLT will be defined as any of the following events that are possibly, probably or definitely attributable to protocol therapy. The DLT observation period for the purposes

THIS PROTOCOL IS FOR RESEARCH PURPOSES ONLY, SEE PAGE 1 FOR USAGE POLICY

of dose-escalation will be the first cycle of therapy.

Dose limiting hematological and non-hematological toxicities are defined differently.

5.5.1 Non-hematological dose-limiting toxicity

5.5.1.1 Any Grade 3 or Grade 4 non-hematological toxicity attributable to the investigational drug with the specific exclusion of:

- Grade 3 nausea, vomiting, diarrhea, or constipation < 3 days duration
- Grade 3 liver enzyme elevation, including ALT/AST/GGT, that returns to Grade ≤ 1 or baseline prior to the time for the next treatment cycle. Note: For the purposes of this study the ULN for ALT is defined as 45 U/L. Adverse event grades will be based on increases above the upper limit of normal, regardless of the subject's baseline. See [Appendix X](#) for toxicity grading table.
- Grade 3 fever < 5 days duration
- Grade 3 infection
- Grade 3 hypophosphatemia, hypokalemia, hypocalcemia or hypomagnesemia responsive to oral supplementation

5.5.1.2 Dose-limiting hypertension

- Any Grade 4 hypertension
- A blood pressure > 25 mmHg above the 95th percentile for age, height, and gender ([Appendix VIII](#)) confirmed by repeated measurement is dose limiting.
- In patients who begin antihypertensive therapy a blood pressure > 10 mmHg but ≤ 25 mmHg above the 95th percentile for age, height, and gender ([Appendix VIII](#)) for > 14 days is dose limiting.

5.5.1.3 Non-hematological toxicity that causes a delay of ≥ 14 days between treatment cycles will be considered dose-limiting.

5.5.1.4 Proteinuria: Urine protein/creatinine (P/C) ratio > 1 and < 1.9 confirmed with a second measurement within 72 hours will be considered a DLT (See [Section 6.5](#))

5.5.1.5 Any gastrointestinal perforation event will be considered a DLT and require removal from protocol therapy.

5.5.1.6 Grade ≥ 2 wound complication or wound dehiscence will be considered a DLT and require removal from protocol therapy.

5.5.1.7 Grade ≥ 3 hepatic failure will be considered a DLT and require removal from protocol therapy.

5.5.1.8 Grade ≥ 2 reversible posterior leukoencephalopathy syndrome (RPLS) will be considered a DLT and require removal from protocol therapy.

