5.5.1.9 Grade ≥ 3 congestive heart failure will be considered a DLT and

THIS PROTOCOL IS FOR RESEARCH PURPOSES ONLY, SEE PAGE 1 FOR USAGE POLICY

require removal from protocol therapy.

5.5.1.10 Any toxicity that is possibly related to the study medication that requires removal from protocol therapy. Note: Allergic reactions that necessitate discontinuation of study drug will not be considered a dose-limiting toxicity.

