6.2 Dose Modifications for Non-Hematological Toxicity

- 6.2.1 Patients who have any dose-limiting non-hematological toxicity (as defined in [Section 5.5.1](#)) may continue on protocol therapy upon meeting eligibility lab requirements or baseline but should receive subsequent infusions at the next lower dose level, except as outlined in Sections [6.4](#) and [6.5](#). Doses reduced for toxicity will not be re-escalated, even if there is minimal or no toxicity with the reduced dose.

THIS PROTOCOL IS FOR RESEARCH PURPOSES ONLY, SEE PAGE 1 FOR USAGE POLICY

6.2.2 If the same non-hematological dose-limiting toxicity recurs after one dose reduction, the patient must be removed from protocol therapy.

6.2.3 Patients who have a dose-limiting non-hematological toxicity that does not resolve to baseline or eligibility criteria within 21 days after the planned start of the next treatment cycle must be removed from protocol therapy.

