6.5 Dose Modifications for Proteinuria

If urinalysis shows \geq trace protein then obtain Urine Protein to Creatinine (UPC) concentrations (See [Appendix IX](#)).

Proteinuria: UPC Ratio	Action
If < 1	Continue protocol therapy
If 1-1.9	Hold next infusion. A second measurement should be obtained within 72 hours. A second confirmation of urine protein/creatinine (P/C) ratio 1-1.9 will be considered a DLT. If resolves to < 1 within 14 days, resume protocol therapy. Subsequent infusions will be given at a lower dose as outlined in Section 6.2 . Monitor the UPC weekly for 2 consecutive weeks once protocol therapy resumes. UPC ≥ 1 that persists ≥ 14 days will require removal from protocol therapy.
If > 1.9	Off protocol therapy

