- ¹ Women of childbearing potential require a negative pregnancy test prior to starting treatment and before starting each subsequent cycle; sexually active patients must agree to use a highly effective method of contraception during protocol therapy and for at least 3 months after the last dose of ramucirumab. Abstinence is an acceptable method of birth control.
- ² Blood pressure will be measured with an appropriate sized cuff at rest. Blood pressure measurement will be repeated within the same day if the blood pressure (BP) is elevated (> the 95th percentile for age, height, and gender). Please note that 3 serial blood pressures should be obtained and averaged to determine baseline BP (See [Section 6.4](#)). If both BP measurements are >95th percentile for age, height, and gender, follow the guidelines in [Section 6.4](#). Patients with elevated BP at any time should have BP measurements performed at least twice weekly until BP is within the 95th percentile for age, height, and gender (See [Appendix VIII](#)).
- ³ If patients have Grade 4 neutropenia then CBCs should be checked at least every other day until recovery to Grade 3 or until meeting the criteria for dose limiting toxicity.
- ⁴ If patients develop Grade 4 neutropenia then CBCs should be checked every 3 to 4 days until recovery to Grade 3.
- ⁵ See [Appendix IX](#) for UPC rationale and calculation and [Section 6.5](#) for dose modifications if UPC > 1. If patient is being followed for prior proteinuria and UPC is obtained at the scheduled time points, urinalysis is not also required. If patient has proteinuria (urine protein/creatinine (P/C) ratio >1), a second measurement should be obtained within 72 hours.
- ⁶ Tumor Disease Evaluation should be obtained on the next consecutive cycle after initial documentation of either a PR or CR. Subsequent scans may restart 2 cycles after the confirmatory scan. Please note that for solid tumor patients, if the institutional investigator determines that the patient has progressed based on clinical or laboratory evidence, he/she may opt not to confirm this finding radiographically. For patients with CNS disease (Part B), ECHO gradient MRI sequences per institutional standards are required to evaluate for hemorrhage (See [Appendix X](#)).

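### Protocol Sections 5.5.1.4 and 6.5 give opposite DLT answers for a confirmed urine protein/creatinine ratio of exactly 1.0 or 1.9 that resolves within 14 days

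*Protocol*

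**What the plan says.** Section 5.5.1.4 of the Protocol makes a UPC "ratio > 1 and < 1.9 confirmed with a second measurement within 72 hours will be considered a DLT" and points to Section 6.5. Both of its bounds are strict.

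Section 6.5 has three rows: below 1 (continue), 1 to 1.9 (hold the next infusion and repeat), and above 1.9 (off protocol therapy). In the middle row, "A second measurement should be obtained within 72 hours" and "A second confirmation of urine protein/creatinine (P/C) ratio 1-1.9 will be considered a DLT". If the UPC falls below 1 within 14 days, treatment resumes at a lower dose. Otherwise, "UPC ≥ 1 that persists ≥ 14 days will require removal from protocol therapy".

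Footnote 5 of the Section 8.1 schedule sends the reader to Section 6.5 "for dose modifications if UPC > 1". It adds: "If patient has proteinuria (urine protein/creatinine (P/C) ratio >1), a second measurement should be obtained within 72 hours".

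Two further clauses use the result. Section 5.5.1.10 counts as a DLT "Any toxicity that is possibly related to the study medication that requires removal from protocol therapy". Section 6.2.1 says that patients with a non-hematological DLT as defined in 5.5.1 "may continue on protocol therapy upon meeting eligibility lab requirements or baseline but should receive subsequent infusions at the next lower dose level", subject to the exceptions in 6.4 and 6.5. Section 6.2.2 removes a patient whose same DLT recurs after one reduction.

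**The concern.** The DLT count is the trial's safety decision variable. Section 11.2.2 defines the MTD by the proportion of patients with a DLT and refers to Section 5.5 for the definition. Section 6.5 also states in terms what is a DLT, and its range is wider at both ends. The cross-reference in 5.5.1.4 does not say which text governs.

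Two things are at stake. First, Part B still uses this definition, so one boundary reading can be counted or not depending on the page consulted. Second, under 6.2.2 a patient already reduced once for proteinuria who later has a confirmed 1.0 that resolves is removed if that reading is a DLT and may stay on if it is not.

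The footnote adds a practical risk. A site working from the schedule would not repeat a UPC of exactly 1.0, although Section 6.5 requires the repeat. The repeat is therefore not missing from the protocol; the schedule simply has a different threshold.

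**Working it through.** The plan gives no figure to reproduce, so the check is to apply each rule to the same readings.

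**Step 1. Identical pairs.** Take a Cycle 1 UPC of *x*, confirmed at the same value within 72 hours, at least possibly related, and falling below 1 within 14 days (for *x* above 1.9 resolution is irrelevant, because 6.5 removes the patient at once).

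- Section 5.5.1.4: DLT if 1 < *x* < 1.9.
- Section 6.5: DLT if 1 ≤ *x* ≤ 1.9.
- Section 5.5.1.10 with 6.5: DLT if *x* > 1.9, through removal.

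| Confirmed UPC | 5.5.1.4 | 6.5 | Result |
|---|---|---|---|
| 0.8, 0.9 | no | no | agree: no DLT |
| 1.0 | no | yes | **conflict** |
| 1.1 to 1.8 | yes | yes | agree: DLT |
| 1.9 | no | yes | **conflict** |
| 2.0, 2.1 | removal | removal | agree: DLT through 5.5.1.10 |

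**Step 2. Mixed pairs.** If both readings must lie in the range, 1.0 then 1.4, or 1.4 then 1.0, is a DLT under 6.5 but not under 5.5.1.4. The same holds with 1.9 in place of 1.0. Pairs strictly inside the range agree. A conflict therefore always needs at least one reading on a bound.

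**Step 3. Does another clause settle it?**

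- 5.5.1.10 needs removal from therapy. A UPC that resolves within 14 days leads to resumption, not removal. If it persists for 14 days or more, removal makes it a DLT whichever range is used.
- 5.5.1.3 needs a delay of at least 14 days between cycles. A hold that ends sooner does not by itself reach this.
- 5.5.1.1 needs Grade 3 or 4. Appendix X grades only bilirubin, ALT, AST and GGT, so the documents show no such route for these values.

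None closes the gap.

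**Step 4. Effect on the count.** The limit in 11.2.2 is fewer than one-third:

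- 1/6 = 0.167 passes; 2/6 = 0.333 does not.
- 3/12 = 0.25 passes; 4/12 = 0.333 does not.

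Two DLTs in six do not automatically fail the dose. If they are of different classes and the other conditions in 11.2.2 are met, expansion to 12 is considered. At most 3 DLTs in 12 are then allowed, so at most 1 more among the next 6. With *X* ~ Bin(6, *p*),

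P(*X* ≤ 1) = (1 − *p*)^6 + 6*p*(1 − *p*)^5.

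| Assumed true DLT rate *p* | Calculation | P(*X* ≤ 1) |
|---|---|---|
| 0.10 | 0.5314 + 0.3543 | 0.886 |
| 0.20 | 0.2621 + 0.3932 | 0.655 |
| 0.30 | 0.1176 + 0.3025 | 0.420 |

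These rates are assumptions. The probabilities show what follows a second DLT of any kind once expansion is opened; they do not measure how often the boundary problem arises.

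**The case against.** The strongest reply is that this is close to editorial.

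- **It will be rare.** Section 9.1.8 lists proteinuria at no more than 3% of patients on single-agent ramucirumab. Taking 3% as an assumption for children, for whom Section 2.4.1 reports no prior experience, the chance of any proteinuria among 6 patients is 1 − 0.97^6 = 0.17, and among 12 it is 1 − 0.97^12 = 0.31. A discordant case must also be related, fall in Cycle 1, involve a bound and resolve within 14 days. It must also arrive when the cohort is one DLT short of the limit. This stands, and it is why the effect is called small.
- **Oversight exists.** A suspected DLT goes to the Study Chair within 24 hours (5.4), dose modifications are notified (6.0), and DLT evaluations are reviewed weekly (14.4.2). This makes silent misclassification unlikely, but it does not tell the Chair which bound to apply.
- **The pointer leads to the safer rule, and 6.5 dictates management of a first event anyway.** Immediate handling is indeed governed by 6.5. The DLT count is not: 11.2.2 refers to Section 5.5.
- **The 6.2.2 consequence needs a chain of events** (a reduction, then a recurrence, with a boundary value involved), and 6.5 has its own removal rules. That is so, but those rules do not cover a recurrence that resolves, and 6.2.2 does.
- **The limit for Part B is inferred.** Section 11.1 foresees expanding Part B to 12 after two different classes of DLT, which implies that the 11.2.2 rule carries over, but no Part B threshold is written out. This stands as an assumption.
- **A two-symbol change to 5.5.1.4 would do.** Inclusive bounds would remove both conflicts in the table. The fuller wording below also covers mixed pairs and states directly what 6.5 and 5.5.1.10 already imply above 1.9.

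**Conclusion.** The concern holds. The two sections give different DLT calls for a confirmed UPC of exactly 1.0 or 1.9, and for pairs with one reading on a bound, when the event is at least possibly related and resolves within 14 days. UPC above 1.9, and boundary values that persist for 14 days or more, are already DLTs through removal.

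The effect is small. Dose escalation is complete, so the remaining exposure is Part B, where the call changes the outcome only at 1/6 against 2/6 or 3/12 against 4/12, assuming the 11.2.2 limit applies there. Patient removal under 6.2.2 can also depend on it. No frequency can be claimed, because the documents give no rounding rule for UPC. If laboratories report one decimal, 2 of the 10 values from 1.0 to 1.9 conflict; with two decimals, 2 of 91. Both are assumptions about reporting and say nothing about how often such values occur.

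It should still be corrected, because it is an error in a decision threshold and costs almost nothing to repair.

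**What to change.** Replace the proteinuria line in 5.5.1.4 with:

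> *UPC ≥ 1 confirmed by a second UPC ≥ 1 within 72 hours, or any UPC > 1.9 (off protocol therapy per Section 6.5), is a DLT.*

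The attribution requirement at the head of Section 5.5 continues to apply. In footnote 5 of the Section 8.1 schedule, change both thresholds from > 1 to ≥ 1. Section 6.5 needs no change; this adopts its more protective bounds.

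The sponsor should add one sentence saying which bound was applied to any patient already assessed at exactly 1.0 or 1.9, so that the reported DLT count can be reproduced. The documents do not show that any such patient exists.

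The cost is one line, two symbols and one sentence, with no change to sample size or procedures.
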